4.4 Subject Early Discontinuation or Withdrawal

Subjects will be advised that they are free to withdraw from the study at any time. In addition, subject participation in this study may be discontinued for any of the following reasons:

- AE
- Lost to follow-up
- Non-compliance with study procedures
- Protocol violation
- Study terminated by Sponsor or other regulatory authorities
- Withdrawal of consent
- Investigator's discretion, including a severe laboratory abnormality or other medical condition that indicates to the Investigator that continued participation is not in the best interest of the subject

Protocol deviations/violations should not lead to subject withdrawal unless they indicate a significant risk to the subject's safety or jeopardise the scientific integrity of the study.

If premature withdrawal from the study occurs for any reason, the Investigator must determine the primary reason and record this information in the case report form (CRF). Additionally, subjects withdrawing after study product administration will undergo all discharge safety procedures as feasible and as deemed necessary by the Investigator.

A subject withdrawn from the study due to any AE or clinically significant abnormal laboratory test values will be evaluated by the Investigator or other qualified individual and will be treated and/or followed up until the symptoms or values return to normal or acceptable levels or until lost to follow-up, as appropriate in the opinion of the Investigator.

Subjects withdrawing or removed from this study cannot re-enter.

4.5 Subject Randomisation

Subjects who complete the study screening assessments and meet all the eligibility criteria and are randomised will be assigned a unique randomisation identification number on Day -1 and will receive study products according to the randomisation scheme generated by Celerion.

The sequences to be used in the randomisation will be ABECD, BCADE, CDBEA, DECAB, and EADBC. 5 subjects will be randomly assigned to each sequence.

If replacement subjects are used, the replacement subject number will be 100 more than the original (e.g., Subject No. 101 will replace Subject No. 1).

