1.3 Study Purpose

This study is being conducted to evaluate the overall performance of [REDACTED] heating device when used with [REDACTED] HTP consumables (stick HHP consumables compared with CC). The study will provide data on nicotine PK, product perception and preference, product usage as measured by topography and tolerability and safety of each of the products compared with subjects' own brand combustible cigarettes (OBCC). The results of this study are intended to contribute to an awareness of the harm reduction potential of the [REDACTED] device when used with i [REDACTED] (ITP) and [REDACTED] (IHP) sticks, and the data may be included in future premarket tobacco application submissions to the Food and Drug Administration Center for Tobacco Products in the United States based on Section 910 of the Federal Food, Drug, and Cosmetic Act - Application for Review of Certain Tobacco Products (FDA 2019).

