6.4.3 Puff Topography

Puff topography will be evaluated over the last 2-hour period during the 4-hour *ad libitum* product use session on Days 1 through 5 as indicated in the Study Events Flow Chart ([Table 1](#)). Following the 4-hour PK blood collection and at the start of their meal, subjects will be allowed to use their assigned study product *ad libitum* for 4 hours. During the last 2 hours of the *ad libitum* session, topography measurements will be taken. The SPA-M device will need to reset at 60 minutes in order to record 2 hours of topography data. Puff parameters will be recorded using SPA-M devices (puff count, puff duration, puff volume, peak puff flow rate, average puff flow rate, inter puff interval) for each product.

The *ad libitum* product use session on Days 1 through 5 will start at approximately the same time each day, with lunch served at the start of the *ad libitum* product use session, at approximately the same time each day. After completion of the *ad libitum* use session (i.e., approximately 8 hours after the start of the morning controlled product use) on Days 1 to 4, subjects will be allowed to smoke their own cigarettes (*ad libitum*) but will abstain from use of any tobacco- or nicotine-containing products for at least 12 hours prior to the start of morning controlled product use session scheduled on the following day.

The topography device will be monitored to ensure the device is actively recording during each session.

Additional details and instructions for puff topography procedures will be provided separately.

Depending on the availability of topography equipment, puff topography may not be performed for some or all assigned subjects.

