#### 5. SUBJECT RANDOMISATION

Subjects who complete the study screening assessments and meet all the eligibility criteria and are randomised will be assigned a unique randomisation identification number on Day -1 and will receive study products according to the randomisation scheme.

The sequences to be used in the randomisation will be ABECD, BCADE, CDBEA, DECAB, and EADBC, with 5 subjects randomly assigned to each sequence.

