# 8.6 Statistical Analysis of Pharmacokinetic Parameters

A linear mixed model for analysis of variance (ANOVA) will be performed on the natural log-transformed PK parameters Cmax and AUCt following the controlled (morning) product use session on each of Days/Periods 1, 2, 3, 4, and 5. The model will include sequence, product, and study period as fixed effects and subject-nested-within-sequence as a random

effect. Sequence will be tested using subject-nested-within-sequence as the error term for informational purposes. Geometric least-squares means (LSM) and 95% confidence intervals (CIs) will be provided for the PK parameters of  $C_{max}$  and AUCt by study product. Geometric LSM ratio, 95% CIs of geometric LSM ratio, and p-values will be provided for the study product comparisons in  $C_{max}$  and AUCt. The comparisons of interest will include each product compared to every other product (pairwise comparisons).

The above statistical analyses will be performed using the following SAS® code:

```
Proc mixed data=<>;
class subject sequence period product;
model \log(\text{parameter}) = \text{sequence period product / ddfm}=KR;
random subject (sequence);
lsmeans product/cl alpha=0.05;
estimate "Product A versus Product E" Product 1 0 0 0 -1/cl alpha=0.05;
estimate "Product B versus Product E" Product 0 1 0 0 -1/cl alpha=0.05;
estimate "Product C versus Product E" Product 0 0 1 0 -1/cl alpha=0.05;
estimate "Product D versus Product E" Product 0 0 0 1 -1/cl alpha=0.05;
estimate "Product A versus Product D" Product 1 0 0 -1 0/cl alpha=0.05;
estimate "Product B versus Product D" Product 0 1 0 -1 0/cl alpha=0.05;
estimate "Product C versus Product D" Product 0 0 1 -1 0/cl alpha=0.05;
estimate "Product A versus Product C" Product 1 0 -1 0 0/cl alpha=0.05;
estimate "Product B versus Product C" Product 0 1 -1 0 0/cl alpha=0.05;
estimate "Product A versus Product B" Product 1 -1 0 0 0/cl alpha=0.05;
run;
```

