# 9.2 Product Evaluation Scale (PES)

The Product Evaluation Scale questionnaire will be completed at 240 minutes for each product use on Days 1, 2, 3, 4, and 5.

Product Evaluation will be considered as a 7-point scale (1 = not at all, 2 = very little, 3 = a little, 4 = moderately, 5 = a lot, 6 = quite a lot, and 7 = extremely). Responses will be presented as the following factor scores:

a) Satisfaction: average of the response scores from questions 1, 2, 3, and 12;

- b) Psychological reward: average of the response scores from questions 4 to 8;
- c) Aversion: average of the response scores from questions 9, 10, 16, and 18;
- d) Relief: average of items 11, 13, 14, 15, and reversed for item 20 (i.e., not at all = 7, extremely = 1);
- e) Items 17, 19, 21 will be summarised as individual item scores.

Descriptive statistics of the subscales will be provided by study product, by sex and overall. Individual responses will be listed by subject.

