# **10. PUFF TOPOGRAPHY**

On Days 1 through 5, puff topography measurements will be performed for a 2 hour period during the last 2 hours of the 4-hour *ad libitum* product use session.

The following per-puff topography parameters will be recorded using Sodim Smoking Puff Analyzer Mobile (SPA-M) devices:

- Puff count
- Puff duration
- Puff volume
- Peak puff flow rate

- Average puff flow rate
- Inter-puff interval

The following per-product topography parameters will then be derived:

- Total number of puffs
- Total puff duration
- Average puff duration
- Total puff volume
- Average puff volume
- Average peak flow rate
- Average flow rate
- Total inter-puff interval
- Average inter-puff interval

Topography parameters will be listed by subject and per-product parameters will be summarised by study product, overall and by sex using descriptive statistics (n, mean, SD, CV%, SEM, minimum, Q1, median, Q3, maximum, and 95% CI).

A linear mixed model for ANOVA will be performed on the per-product topography parameters (no data transformation). The model will include sequence, product, and study period as fixed effects and subject-nested-within-sequence as a random effect. Sequence will be tested using subject-nested-within-sequence as the error term for informational purposes. LSMs and 95% CIs will be provided for the parameters by study product. LSM differences, 95% CIs of LSM differences, and p-values will be provided for the study product comparisons in per-product topography parameters. The same comparisons from PK analysis detailed above will be used.

The ANOVA analysis will be performed using the same SAS® code as outlined in the Statistical Analysis of Pharmacokinetic Parameters section above.

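### Do the five randomisation sequences leave the product comparisons exposed to carryover that the plan should have balanced or modelled?

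*Protocol*

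**What the plan says.** Protocol 4.5 fixes the list: "The sequences to be used in the randomisation will be ABECD, BCADE, CDBEA, DECAB, and EADBC". The SAP (section 5) repeats it: the sequences "will be ABECD, BCADE, CDBEA, DECAB, and EADBC, with 5 subjects randomly assigned to each sequence". The model for Cmax and AUCt (SAP 8.6) is described as follows: "The model will include sequence, product, and study period as fixed effects and subject-nested-within-sequence as a random" effect. It contains no term for the previous day's product. SAP 9.1 uses the same model for urge to smoke, and SAP 10 uses it for topography, where "The same comparisons from PK analysis detailed above will be used". That means all ten pairwise contrasts, with p-values. The only order-related test is the informational sequence test.

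The Product Evaluation Scale is described but not tested (SAP 9.2): "Descriptive statistics of the subscales will be provided by study product, by sex and overall". Intent to Use is treated the same way (SAP 9.3). Protocol 4.3.5 allows own-brand smoking after each day's assigned session, followed by at least 12 hours without nicotine. Topography covers the last 2 hours of the 4-hour ad libitum session, and Protocol 6.4.3 warns that "puff topography may not be performed for some or all assigned subjects".

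**The concern.** A Williams design for an odd number of products needs two squares before every product follows every other equally often. Only one is used here. Read off the list, A is followed only by B and D, B by C and E, C by A and D, D by B and E, and E by A and C. With no carryover term in the model, an effect of yesterday's product on today's puffing would be partly read as a product difference. The sequence test would not reveal it, because it compares subjects and barely responds to first-order carryover. Topography is the exposed outcome: it has no baseline adjustment, all ten contrasts are tested, and the second square appears to cost nothing. At stake would be spurious differences, or masked real ones, in how subjects puff on the products.

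**Working it through.** **Inputs.** Five sequences with 5 subjects each, so N = 5 × 5 = 25, matching the protocol. Five periods. Half-life 2 h (Protocol 7.3.1). Abstinence at least 12 h (Protocol 4.3.5). The carryover size L is not in the documents, so results are given per unit of L or for assumed values in within-subject SD (σ).

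**Balance.** Each product occurs once per subject and five times in each period, so a product difference is a difference of two means of 25 observations. Its variance is 2σ²/25 = 0.080σ². Each ordered pair that occurs does so 10 times.

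**Shift in the planned design, one source product.** Suppose only E carries over. E precedes A in 10 of A's 25 observations, and likewise C, so both means move by 10/25 = 0.40L. B, D and E do not move. Contrasts between {A, C} and {B, D, E}: 2 × 3 = 6 shift by 0.40L and four do not. The mean over ten is 6 × 0.40/10 = 0.24L. The pattern is the same for any other single source.

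**Shift with both squares.** Keep N = 25, with 3 subjects on each listed sequence and 2 on each reversal. E then precedes A and C 6 times each and B and D 4 times each: 6/25 = 0.24L and 4/25 = 0.16L. Two contrasts shift by 0.24L, two by 0.16L, four by 0.08L and two by 0. The mean is (0.48 + 0.32 + 0.32)/10 = 0.112L, and eight contrasts are affected.

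**Comparisons against E.** Protocol 1.3 sets out to obtain "product usage as measured by topography and tolerability and safety of each of the products compared with" own-brand cigarettes. Carryover by product type is more natural than carryover from one flavour but not from its sibling. Mean absolute shift over A–E, B–E, C–E and D–E:

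| Source of carryover | Planned square | Both squares, 15/10 |
|---|---|---|
| Cigarette | (0.40+0+0.40+0)/4 = 0.20L | (0.24+0.16+0.24+0.16)/4 = 0.20L |
| Both HTPs equally | (0.40+0+0+0)/4 = 0.10L | (0.24+0.16+0+0)/4 = 0.10L |
| Both HHPs equally | (0+0+0.40+0)/4 = 0.10L | (0+0+0.24+0.16)/4 = 0.10L |
| All four heated products equally | 0.20L | 0.20L |
| All five equally | 0 | 0 |

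The largest shift against E falls from 0.40L to 0.24L in the first four rows. For HTP-type or HHP-type carryover, the number of affected contrasts among all ten rises from four to seven.

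**Which outcomes are exposed.**

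- Cmax and AUCt: residual nicotine is at most 2^(−12/2) = 1.6% of its level when abstinence starts, and the decayed pre-use level is subtracted.
- Urge Emax and AUEC: changes from a baseline taken the same day.
- Product Evaluation Scale and Intent to Use: no test to distort.
- Topography: the assigned session ends about 8 h after morning use, and recording next day starts about 6 h after morning use. The gap is 24 − 8 + 6 = 22 h. It includes optional own-brand smoking, the abstinence, controlled use of the new product and 2 h of its ad libitum use.

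**Size if it occurred.** The standard error of a contrast is √0.080 = 0.28σ. For cigarette carryover of 0.25, 0.5 and 1.0σ, the planned A–B contrast shifts by 0.10, 0.20 and 0.40σ. The simulated error rate of its nominal 5% test is 6.4%, 10.5% and 25.4%.

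**The case for a change.** The strongest case for change is that the second square keeps N = 25 and the contrast variance of 0.080σ². For single-source carryover it more than halves the mean shift over all ten contrasts (0.24L to 0.112L). It also makes a full carryover adjustment cheap, at 6–7% extra variance instead of 40–91%. SAP 1 treats exploratory analyses it does not name as out of scope, so a later check would look data-driven. If the list must stay, one prespecified exploratory model for topography would at least bring the issue into view.

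The arithmetic stands, but it does not show a defect. For cigarette carryover the gain falls among the heated products: the mean over the six contrasts among A–D drops from 0.27L to 0.05L. The mean against the cigarette stays at 0.20L, and B–E and D–E go from 0 to 0.16L. The change would also create ten sequence groups of 2 or 3 subjects and cut the error degrees of freedom of the sequence test from 25 − 5 = 20 to 25 − 10 = 15. Table 1 footnote h of the protocol and the five-column disposition, demographic and smoking-history shells in SAP 15.2 would have to be rewritten.

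The analysis-only alternative is weak. An indicator for a cigarette on the previous day has a standard error of 0.31σ, so power is 13% at 0.25σ and 36% at 0.5σ, reaching 89% only at 1.0σ. It covers one source product only. Over nine topography parameters, if independent, the chance that at least one 95% interval excludes zero by chance is 1 − 0.95⁹ = 37%. It would change no planned result, and Protocol 7 already lets additional analyses be added to the plan.

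**Conclusion.** The concern does not hold. One Williams square, with products balanced over periods and no carryover term, is a legitimate design. The protocol and SAP agree on it and promise nothing that it fails to deliver. The primary Cmax and AUCt comparisons are expected to be negligibly affected.

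The remaining exposure is a possible behavioural carryover in a secondary outcome that may not be collected in everyone: 0.40L in six of ten contrasts for a single source, 0.40L in four for HTP-type or HHP-type carryover, and none if all products carry over equally. Using both squares trades a lower maximum (0.24L) for more affected contrasts, with no average gain against own-brand cigarettes when carryover follows product type. Statisticians could reasonably choose either.

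This rests on the stated 2-hour half-life, adherence to the 12-hour abstinence, and first-order, additive carryover. The documents give no value for L. A carryover near 1σ would distort the topography tests materially, but nothing in the documents suggests one.

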5. STUDY PRODUCTS/MATERIALS

5.1 Description of Study Products

All subjects will use Products A through E.

The following study products will be used in this study:

| Product Designation | Product Type | Study Product Name |
|----------------------------|---------------------|--|
| A | HTP | [REDACTED] |
| B | HTP | |
| C | HHP | |
| D | HHP | |
| E | Cigarette | Subject’s own brand combustible cigarette (OBCC) |

HTP, heated tobacco product

HHP, heated herbal product

5.1.1 Own Brand Combustible Cigarettes

Subjects will be required to bring with them to the CRU a sufficient supply (i.e., 6-day supply in unopened packs) of their OBCCs for personal use throughout confinement.

5.1.2

[REDACTED]

[REDACTED] controlled heater (Figure 2). The handheld device heats the tobacco using an electronically controlled heating rod. The rod can be set to 2 temperatures: 'mild' mode (315°C) or 'Intense' mode (345°C). The handheld device supplies heat to the tobacco/herbal substrate portion of the respective stick [REDACTED] using the heating rod for 5 minutes. The heating device must be recharged after 25 consecutive uses.

[REDACTED]

[REDACTED]

5.2 Study Product Accountability and Dispensing

[REDACTED] devices, [REDACTED] tobacco sticks, and [REDACTED] herbal sticks, will be provided by the Sponsor. The CRU staff will coordinate shipping of products and devices from the Sponsor. The staff will document the date each shipment was received and recorded in the inventory records. The CRU staff will document and reconcile the total number of products shipped to the CRU, the total number of products dispensed during the study, and the total number of products remaining at the end of clinical conduct. Subjects will bring a 6-day supply (unopened packs) of their OBCCs for personal use at designated times throughout confinement in the

CRU.

For each day of HTP/HHP product use, subjects will be provided with a new/unused device to be used for the morning controlled product use and *ad libitum* product use sessions. A fresh stick will be provided at the start of the morning controlled product use session and at the start of puff topography.

All products will be stored in a locked, limited-access area at the CRU and kept at controlled room temperature (defined as 20-25°C [68-77°F], with excursions permitted to 15-30°C [59-86°F]). Humidity is recorded but not controlled.

Study products for dispensing (including OBCC) to subjects will be prepared by the study staff according to instructions provided by the Sponsor. Individual study product dispensing records will be maintained by the CRU staff for each subject. Care should be taken when repackaging the study products for use at the CRU to avoid exposure to air and moisture to the extent possible. The pharmacy will maintain records of the number of cigarettes dispensed for each subject.

The study staff will document the start time and stop time of each product use session. The number of HTP/HHP sticks used and cigarettes smoked will be documented during each *ad libitum* product use session on Days 1 through 5. The number of cigarettes smoked will be documented on Day -1 prior to smoking abstinence (at least 12 hours prior to the start of morning controlled product use session on Day 1), and on Days 1 through 4 following the 4-hour *ad libitum* product use session until at least 12 hours prior to the start of morning controlled product use session scheduled on the following day.

Subjects will smoke their OBCC and use each assigned product only in designated areas of the CRU.

Opened and unopened packages of [REDACTED] devices and [REDACTED] sticks will be returned to the Sponsor or destroyed at the direction of the Sponsor. Opened and unopened packages of subject's OBCC will be returned to the subjects at the end of the study. All returns or destruction of study products will be documented.

The [REDACTED] device has two power settings: 'intense' mode (345°C heating rod temperature) and 'mild' (315°C heating rod temperature). **Subjects should use the device set on the 'intense' mode during both the defined use and *ad libitum* use sessions.**

Immediately prior to use of the HHPs ([REDACTED]) the filter section of the [REDACTED] sticks must be pressed firmly between the fingers in order to crush the capsule in the filter [REDACTED] according to the product use instructions. This applies to both the defined use and *ad libitum* use sessions, and also to the product trial session on Day -1.

6. STUDY PROCEDURES

6.1 Screening

Potential subjects will undergo Screening procedures to ensure that they meet the requirements for inclusion in the study within 28 days prior to study procedures on Day -1.

Screening procedures will be performed as delineated in the Study Events Flow Chart (Table 1).

6.1.1 Informed Consent

All prospective subjects will have the study explained by the Investigator or his/her designee and will be required to read, sign, and date an ethics committee (EC) approved ICF prior to completion of screening or other study procedures. This consent form will provide the subjects in non-technical terms with the purpose of the study, procedures to be carried out, and potential hazards. The subjects will be assured that they may withdraw from the study at any time without jeopardising medical care related to or required as a result of study participation. Subjects will be given a copy of their signed ICF.

6.1.2 Medical History/Demographic Data/Record of Concomitant Medication

Medical history and socio-demographic data, including name, sex, age (each subject must show proof of age with government-issued identification [e.g., driver's license]), National Insurance number, race, ethnicity, address, and phone number will be recorded at Screening for each subject.

Any concomitant medications taken from 30 days prior to Check-in through discharge will be recorded in the CRF and source document.

